1.1 SPECIFIC AIMS

1.1.1 Primary Aims

Aim 1: To determine the overall subject retention rate of Stage 1 and Stage 2.

1a. Stage 1: The proportion of subjects in each arm who complete all study visits from baseline to 4 ± 1 week.

1b. Stage 2: The proportion of subjects who complete all study visits from baseline to 24 ± 3 weeks.

Aim 2: To determine the MTM intervention adherence rate in Stage 2 as assessed using the 24-hour Diet Recall interview and/or the VioScreen FFQ.

2a. Stage 2: The proportion of subjects who consume $\geq 75\%$ of delivered meals and evening snack from baseline to 9 ± 2 weeks.

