2. STUDY DESIGN

Overview: We propose a two-stage trial to determine the feasibility of MTM intervention in cirrhosis patients with a history of HE. Stage 1 will assess the feasibility of 10 different assessments and 2 weeks of MTM among three different cirrhosis populations, 1) patients with a history of \geq Grade 2 HE, 2) patients with a history of moderate to severe ascites and 3) patients with compensated cirrhosis to determine if any of the feasibility concerns are specific to particular cirrhosis complications. Patients from each group will be enrolled in equal proportion with a total of at least 30 subjects. Baseline assessments will be conducted in person at baseline and at the final study visit after completion of 2 weeks MTM intervention at 4 ± 1 weeks.

Figure 1. Stage 1 Study Design

Stage 2 is a pre-post trial after refining selection of assessments based on subject ability to complete procedures and detect changes in outcomes of Stage 1. We will enroll at least 20 subjects with a history of \geq Grade 2 HE. This stage begins with a 4 ± 1 week run-in phase with patients enrolled in person or via phone. Patients are observed in this run-in period to demonstrate interest in completing the study. Subjects will return to the clinic for a study visit in order to complete baseline assessments. Subjects in Stage 2 subjects will receive 6 weeks of MTM. During the intervention phase, subjects will receive weekly phone calls and will also be required to complete dietary recall assessments in order to measure whether they are consuming the MTM. After completion of MTM intervention, subjects will return to the clinic for an in person visit where they will repeat all baseline assessments. Thereafter, there is a 12-week observational period. Subjects will complete their final study visit and exit interview via phone between Weeks 21 and 27; Study Days 150 – 194 (SD 172 \pm 22) in order to complete final assessments.

Figure 2. Stage 2 Study Design

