ZonePerfect Classic protein bars are shelf stable and contain 10 - 15g of protein per serving (1 bar). They do not contain any artificial sweeteners, flavors or colors. They come in the following flavors: strawberry yogurt, chocolate mint, oatmeal chocolate chunk, chocolate caramel cluster and others. Additional information can be found here: <https://zoneperfect.com/products>

The Perfect Bar is a refrigerated protein bar 14 – 17g of protein per serving (1 bar). Their primary source of protein are nut butters. They do not contain any artificial sweeteners, flavors or colors. Many of the flavors are lower in sodium (30-50g per serving), so these will function as a good option for subjects with ascites. They come in the following flavors: peanut butter, almond butter, blueberry cashew, mocha chip, among other. Additional information can be found here: <https://perfectsnacks.com/collections/bars>

There are two options for the nighttime supplement. The first option is a protein powder that can be dissolved in either water or milk. We are providing subjects with ProCel Chocolate Whey Protein powder which provides 15g of protein per serving. The second option is a liquid protein that can be mixed in a cup of water. We are providing subjects with LiquaCel Packets (assorted flavors) of liquid protein which provides 16g of protein per serving. Additional information regarding the protein supplements can be found here: <https://globalhp.com/shop/>

Once the MTM order is placed, subjects will receive meals at home within 3 – 5 days. The MTM will be pre-packaged for storage with preparation (typically microwave heating). Subjects are instructed to start eating the meals and protein supplements the day after they receive the meals from PurFoods. Subjects will consume meals and supplements daily for 6 weeks. Subjects will consume meals between approximately Weeks 4 – 11 of the study (SD 32±8 – 74±8). The actual dates of MTM for each subject will be dependent upon the date they complete their baseline appointment. During the final two weeks of MTM, subjects will undergo the 24-hour Diet Recall on two separate occasions, once either on a Tuesday or Wednesday and once on a Sunday or Monday in order to capture weekday and weekend behaviors. The study coordinator will call the subject to confirm the

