date the subject started eating the meals and protein supplements, the diet recalls will occur within 28 to 42 days from this date. The date the 24-hour Diet Recall is completed is dependent upon the actual dates of the final two weeks of the intervention and this will vary per subject, but it will be completed between Weeks 8 – 11 for all subjects (SD 67±14). The dietitian will attempt to contact subjects via phone up to 4 times to complete the dietary interviews. The study coordinator will solicit questions related to dietary concerns during telephone calls once per week with each subject during the intervening weeks. The coordinator will also ask the subject if they know their current weight, and confirm that they have been eating the MTM.

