	Entry/ Day 1*	RUN-IN → BASELINE		INTERVENTION			FU 1	OBSERVATION	FU 2
		STUDY DAYS							
		11 (± 9 days)	28 (± 7 days)	32 (± 8 days)	67 (± 7 days)	74 (± 8 days)	81 (± 15 days)	81 (± 15 days) → 165 (± 15 days)	172 (± 22 days)
Informed Consent	X								
Demographics Questionnaire	X								
SF-8			X				X		X
PROMIS Self-Efficacy			X				X		
EncephalApp			X				X		
Liver Frailty Index			X				X		
Animal Naming Test			X				X		X
PROMIS Instrumental Support			X				X		
Health History Questionnaire	X								
24-hr Diet Recall		2x			2x				
VioScreen FFQ			X				X		
Phone Call/Interview				6x				6x	X
Medically Tailored Meals				X → X					
Healthcare Utilization	CHART REVIEW →								X

* Study Day 1 is defined as the calendar day on which the subject is enrolled/consented into the study.

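### The primary Stage 2 adherence endpoint (at least 75% of delivered meals and evening snack) rests on two late recall days and/or a 90-day food-frequency questionnaire, and neither measures that share over the course

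*Combined protocol and SAP*

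**What the plan says.** Section 1.1.1, Aim 2, is "To determine the MTM intervention adherence rate in Stage 2 as assessed using the 24-hour Diet Recall interview and/or the VioScreen FFQ". Aim 2a turns this into a proportion of subjects who consume at least 75% "of delivered meals and evening snack from baseline to" 9±2 weeks. Sections 1.2 and 4.3.3 list the rate as a primary Stage 2 endpoint.

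- **Recalls.** Section 2 has subjects "complete dietary recall assessments in order to measure whether they are consuming the MTM". Section 4.3.2 schedules them: "During the final two weeks of MTM, subjects will undergo the 24-hour Diet Recall on two separate occasions". Counting from the confirmed first day of eating, "the diet recalls will occur within 28 to 42 days from this date". The other two Stage 2 recalls fall in the run-in, before any meals (Section 4.3.1).
- **VioScreen FFQ.** Section 4.1, item 7, describes nutrient and food-use reports for the previous 90 days, from about 155 general food and beverage items. It is completed within two weeks after the meals end (Section 4.3.3).
- **Weekly calls.** Section 4.3.2 provides "telephone calls once per week with each subject during the intervening weeks", in which the coordinator will "confirm that they have been eating the MTM". Table 2, row "Phone Call/Interview", shows six during the intervention. Aim 2 does not name them, and no quantity is described.

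Section 6.2.1 does not say how recall or FFQ data become a percentage of delivered items. The protocol does not define the evening snack, and it does not say whether the daytime bar counts.

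**The concern.** Aim 2a needs a numerator (items eaten) and a denominator (items delivered) for each subject over the whole course. The recalls give a small sample taken only late in the course. The FFQ mixes meal days with other days and, as described, does not identify study meals. The wording still lets either instrument decide, with no rule for choosing or combining them.

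Section 1 gives Stage 2 the task of evaluating fidelity and adherence ahead of a definitive trial, so this rate is what that trial would plan from. Subjects near 75%, or whose eating changes over the six weeks, can be put in the wrong class. The resulting shift in the rate is a bias, which enrolling more subjects would not remove.

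**Working it through.** The plan gives no adherence estimate, target or power figure to reproduce; Section 6.1 bases the sample size on clinical judgement.

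**Coverage (from the documents).**
- Course: 6 × 7 = 42 days (Section 4.3.2).
- Recall days: 2/42 = 4.8%. Days 1 to 28 (28/42 = 67%) are never sampled.
- FFQ: at most 42/90 = 46.7% of the look-back is on meals.

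**Timing, before any sampling error.**
- 60% in weeks 1–4, then 100%: (28×0.6 + 14×1)/42 = 73.3%. This is truly non-adherent, but both recalls show full intake, so the subject is scored adherent.
- 100%, then 60%: (28×1 + 14×0.6)/42 = 86.7%. This is truly adherent, but both recalls fall in the 60% period. With 2, 3 or 4 items a day the subject is scored non-adherent with probability 0.525, 0.767 or 0.685.

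**Sampling error with steady eating.** Items per day are not stated, so k = 2 to 4 is assumed. Two recalls observe n = 2k items, and a subject is scored adherent if X ≥ 0.75n, with X ~ Binomial(n, p). The cuts are 3 of 4, 5 of 6 and 6 of 8. At k = 3 the effective cut is therefore 5/6 = 83%.

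| True share p | k = 2 | k = 3 | k = 4 |
|---|---|---|---|
| 60% (should fail) | 0.475 | 0.233 | 0.315 |
| 80% (should pass) | 0.819 | 0.655 | 0.797 |
| 90% (should pass) | 0.948 | 0.886 | 0.962 |

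Entries are P(scored adherent). If items within a day are correlated (0.3 to 0.6, k = 3 or 4), the 60% eater passes 30–39% of the time.

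**Group level.** The documents give no distribution of adherence. The assumption is Beta with mean 0.50 to 0.90 and concentration 5 or 10. The misclassified share is the integral over p of P(wrong class | p). The shift is the scored rate minus the true rate.
- k = 3–4: 8–29% misclassified, shift −7 to +21 points.
- k = 2: the extremes are 38% and +32 points.
- Mean 0.90, any k: 8–13% misclassified.

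**Would a count do better?** Model the reported share as true share + bias + Normal(0, SD), with the same Betas.
- SD 5 points, no bias: 3–11% misclassified, fewer than the recalls in every scenario.
- SD 10 points, no bias: 7–20%. At mean 0.90 this is about level with the recalls (8–10% against 8–13%).
- Bias in the rate, SD 5: at means 0.70–0.80 and k = 3, over-reporting by up to about 3 points already makes the count more biased than error-free recalls. A 10-point over-report adds 13–25 points to the rate at means 0.50–0.80.

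**The case against.** The strongest reply is that this is a pilot of at least 20 subjects with no adherence target. The exact 95% interval for 15/20 is 51–91%, wider than most of the shifts above. Subjects far from 75% are mostly classed correctly. Recalls are run by trained dietitians with output per food and per meal (Section 4.1, item 10), so items could be identified on the two days sampled. Stage 1 tries both instruments, and Section 4.2.3 lets its results change the Stage 2 assessments.

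Much of that stands, and it limits the severity. It does not cure the written definition. Accurate recall of two late days says nothing about weeks 1–4, and no rule links recalled foods to delivered items. The Stage 1 review is not directed at this endpoint.

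A reader might infer three stronger things that the documents do not support:
- **That intake is not checked at all.** Section 2 gives the recalls that purpose, and the weekly calls ask about eating. Case report form fields are not shown (Section 7.1), so silence in the text does not prove that no count is recorded.
- **That the rate will be wrong by 30 points or more.** That size arises only at an assumed two items a day.
- **That weekly counts are simply superior.** They are self-reports to a coordinator by people with recent HE, with unknown error. Their advantage is clear for classifying subjects but not assured for bias in the rate.

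**Conclusion.** The point holds and should be fixed, with medium confidence. The design gap rests on the documents alone: two of 42 days, none in weeks 1–4, an FFQ that as described cannot give eaten over delivered, and wording that lets it decide. The sizes rest on assumptions about items per day, independence and the Beta distributions. At 3–4 items a day they are 8–29% misclassified and a shift of −7 to +21 points. They give the recalls no reporting error and, at group level, assume steady eating, which favors the recalls.

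Harm is small if adherence is near 90%. The documents offer no estimate, and the Significance section reports severe anorexia in most patients with cirrhosis. No stated decision turns on the rate; what is at stake is its value for planning the definitive trial.

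**What to change.** Amend before Stage 2 enrolls, by the route in Section 8.1.

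1. Remove the FFQ from Aim 2 and keep it for nutritional intake.
2. At each of the six weekly calls, record delivered meals and evening snacks eaten and left over since the last call, reconciled with deliveries. Define adherence as total eaten divided by total delivered over the subject's own course; adherent if at least 75%. Section 4.5 has meals stored during a hospital stay and resumed afterward, so stored items stay in the denominator and are counted when the course resumes. No days are subtracted.
3. Have the two dietitian recalls flag study items, and report the recall-based rate beside the count-based rate as a prespecified check on over-reporting.
4. Report the count-based rate on counted weeks, with bounds treating uncounted items as all not eaten and as all eaten. Scoring them only as not eaten would turn missed calls into non-adherence. With equal weekly deliveries, one uncounted week would require 0.75×6/5 = 90% in the other five, and two would cap the share at 4/6 = 66.7%.
5. State what the evening snack covers and whether the daytime bar counts.

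The cost is four count fields in an existing call script (meals and snacks, eaten and left over), slightly longer calls, and rewording of Aims 2 and 2a. Counting may itself raise adherence, so the definitive trial would need the same calls for the rate to carry over. Because the error in the counts is unknown, neither rate should be reported alone.

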1.1.2 Secondary Aims

Secondary aims of this trial will include feasibility of study procedures:

Aim 3: To determine the proportion of subjects who complete all 24-hour Diet Recall interviews in Stage 1 and Stage 2.

3a. Stage 1: The proportion of subjects in each arm who complete the 24-hour Diet Recall between Study Days 9 and 17.

3b. Stage 2: The proportion of subjects who complete all four 24-hour Diet Recalls at baseline and 9 weeks.

Aim 4: To determine the proportion of subjects who complete all study procedures and assessments in Stage 1 and Stage 2.

4a. Stage 1: The proportion of subjects who complete all study procedures and assessments at baseline and Week 4 ± 1 visit.

4b. Stage 2: The proportion of subjects who complete all study procedures and assessments at baseline, Week 11 and Week 24 ± 3 visits.

Aim 5: To determine the time required for Stage 1 subjects to complete each study procedure at baseline and the Week 4 ± 1 end of study visit.

5a. Stage 1: The time required, measured in minutes and seconds, for subjects to complete each individual assessment at baseline and Week 4 ± 1 , and the total time required to complete both study visits.

Aim 6: To determine the number of eligible candidates formally screened within 6 months of study start date, and the percentage of eligible candidates who were recruited and enrolled into Stage 1 and Stage 2.

6a. Stage 1 & 2: The total number of eligible subjects and percentage of those recruited and enrolled within 6 months of start date as tracked in a study specific screening log.

Aim 7: To determine the drop-out rate of subjects in Stage 1 and Stage 2.

7a. Stage 1 & 2: The percentage of enrolled subjects who drop-out of either study stage before the final study visit due to withdrawal by subject or lost to follow-up, and not due to death, withdrawal by study staff or PI discretion.

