Procedures	
 - Stage 1 & Stage 2: Screen for patients with cirrhosis and recent episode of overt HE and/or ascites. - Consent eligible patients. - Stage 1: Feasibility of assessments 
 • Complete baseline assessments in-person • Subjects receive a nutrition education hand-out and 2 weeks of MTM. They undergo 24-hour dietary recalls during this intervention phase. • Subjects complete final study visit at 4\pm1 weeks in-person and complete all assessments - Stage 2: Pre-Post trial after refining selection of assessments based on patient ability to complete and detect changes from Stage 1. 
 • After enrollment, there is a 4\pm1 run-in phase to demonstrate interest • Subjects return for in-person visit to complete baseline assessments • Subjects receive a nutrition education hand-out and 6 weeks of MTM. They undergo 24-hour dietary recalls during this intervention phase. • Subjects return for in person visit at 11\pm2 weeks and complete all assessments. There is a 12-week observational period. • Subjects complete final study visit at 24\pm3 weeks via phone.
Primary Outcomes	
 1. Overall subject retention rate, defined as subjects who complete all study visits (Stage 1 & Stage 2). 2. Subject adherence rate to MTM intervention (Stage 2 only).
Secondary Outcomes	
 1. Proportion of subjects who complete all study assessments and procedures. 2. The time required to complete assessments (Stage 1 only). 3. The number of eligible candidates screened and proportion of those enrolled. 4. Subject drop-out rate.
Exploratory Outcomes	
 1. Determine if MTM improves the subject's nutritional intake (Stage 2 only). 2. Determine if MTM affects the subject's cognitive function or health-related quality of life (HRQOL) (Stage 2 only). 3. Explore whether MTM affects clinical outcomes and healthcare utilization rates (Stage 2 only). 4. Patient satisfaction and preferences of MTM (Stage 2 only).

Table of Contents

SIGNIFICANCE	5
1. STUDY OBJECTIVES	6
1.1 Specific Aims	6
1.1.1 Primary Aims	6
1.1.2 Secondary Aims	6
1.2 Exploratory Outcomes	7
1.3 End Points	8
2. STUDY DESIGN	8
3. SELECTION AND ENROLLMENT OF SUBJECTS	9
3.1 Inclusion Criteria	9
3.2 Exclusion Criteria.....	11
3.3 Study Enrollment Procedures	11
3.3.1 Identification & Recruitment.....	11

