3.3 STUDY ENROLLMENT PROCEDURES

3.3.1 Identification and recruitment

After IRB approval, we will obtain informed written consent for participation from at least 50 subjects (up to 80 subjects) at the University of Michigan Health System (UMHS). However, if we are required to move to remote procedures, we will obtain verbal consent via phone with a waiver of documentation. Stage 1 will enroll up to 30 subjects and Stage 2 will enroll at least 20 subjects. If subjects drop-out, withdrawal or become lost to follow up before the final study end point, the study team will enroll additional subjects to account for the loss. Patients will be identified by one of 5 methods: 1) referral by UMHS Liver Clinic providers, 2) screening of clinic schedule on the outpatient or transplant liver service, 3) referral from study coordinators of pre-existing registry studies at UMHS, 4) screening of hospitalized patients and 5) screening of patients scheduled for paracentesis or endoscopy in their respective procedure rooms. The PI will review all potential patients before the study coordinator approaches the patient to verify eligibility.

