4.2 STAGE 1 PROCEDURES**4.2.1 Enrollment & Baseline**

For Stage 1, subjects will be primarily consented and enrolled in person at the time of a previously scheduled appointment or procedure. All subjects will provide their contact information and complete baseline assessments in person on the date of enrollment. The date subjects complete the baseline assessments is Study Day 1. If we are conducting procedures remotely, consent and baseline assessments will be completed with subjects via phone by a study coordinator. The study coordinator will track and document the amount of time it takes for subjects to complete each assessment. The total time includes the amount of time it takes to provide instruction to the subject, the amount of time it takes for the subject to answer all questions or complete all performance measures and any additional time required to answer questions the subject has. If the assessments will be completed with subjects in person, they will be conducted in the following order:

1. Demographics Questionnaire

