4.3 STAGE 2 PROCEDURES

4.3.1 Enrollment & Baseline

For Stage 2, subjects will be primarily consented and enrolled in person at the time of a previously scheduled appointment or procedure or via phone. If we are conducting procedures remotely, consent will be completed with subjects via phone by a study coordinator. Subjects will complete the Demographics and Health History questionnaire after informed consent procedures are

completed, and will also provide their contact information. The date that subjects consent is Study Day 1.

After enrollment, there is a run-in phase until 4+1 (28+7 days) weeks prior to implementation of the MTM intervention. Between Study Days 2 and 20 (11+9 days) of the run-in phase, subjects will undergo the 24-hour Diet Recall on two separate occasions, once either on a Tuesday or Wednesday and once on a Sunday or Monday in order to capture baseline weekday and weekend behaviors. A registered dietician from the University of Michigan Nutrition Obesity Research Center will call the subject directly in order to conduct the 24-hour Diet Recall via phone.

Baseline assessments will be conducted with all subjects at the end of the run-in phase within the 4+1 (28+7 days) weeks window. The study coordinator will complete assessments 1 – 6 in person with the subject. The subject will be provided the resources (website link and login information) during their study appointment to be able to complete the VioScreen FFQ at home within 1 day of their baseline visit. If a subject does not complete the baseline appointment in person, the subject will be withdrawn by study staff at that time. The assessments will be completed with each subject in the following order:

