5. ANT
6. PROMIS IS
7. VioScreen FFQ

If the assessments will be completed with subjects remotely via phone, the EncephalApp Stroop and Liver Frailty Index will not be conducted. They will be conducted in the following order:

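### Stage 2 subjects who simply miss the in-person baseline are coded as staff withdrawals, so the Aim 7a drop-out rate does not count them

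*Combined protocol and SAP*

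**What the plan says.** The Summary lists "Subject drop-out rate" among the secondary outcomes. Aim 7a (Section 1.1.2) defines it for both stages as a percentage of enrolled subjects. It counts those who leave before the final visit "due to withdrawal by subject or lost to follow-up, and not due to death, withdrawal by study staff or PI discretion".

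Stage 2 subjects are enrolled when they consent, which is Study Day 1 (Section 4.3.1). A run-in of about four weeks follows, and Section 2 gives its purpose: "Patients are observed in this run-in period to demonstrate interest in completing the study". Baseline closes the run-in, and Section 4.3.1 sets the consequence of missing it: "If a subject does not complete the baseline appointment in person, the subject will be withdrawn by study staff at that time". The same section also gives an order of assessments for a phone baseline: "If the assessments will be completed with subjects remotely via phone, the EncephalApp Stroop and Liver Frailty Index will not be conducted".

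Stage 1 has no such interval. Section 4.2.1 says: "All subjects will provide their contact information and complete baseline assessments in person on the date of enrollment".

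Two other passages bear on the point. Section 3.3.1 provides for replacement: "If subjects drop-out, withdrawal or become lost to follow up before the final study end point, the study team will enroll additional subjects". Aim 1b (Section 1.1.1) defines Stage 2 retention, a primary outcome: "The proportion of subjects who complete all study visits from baseline to 24 ± 3 weeks". It names no denominator.

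**The concern.** The run-in is where weak commitment should show itself, and the plainest sign is a subject who consents and then does not come to baseline. The plan directs staff to withdraw that subject, and Aim 7a excludes staff withdrawals. The subject stays in the enrolled denominator and never reaches the numerator. More no-shows therefore leave the drop-out rate flat, or lower it if they are replaced and the denominator grows.

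The pilot is meant to show whether a definitive randomized trial is feasible. Subjects who consent and then vanish are part of that answer, and Aim 7a is the outcome that separates loss of engagement from death and administrative exits. The one definition also behaves differently by stage, because Stage 1 does baseline on the day of enrollment and this route out does not arise there.

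**Working it through.** The plan states no expected drop-out rate, so there is no figure to reproduce. The check has two parts: how the rules classify a no-show, and how far the reported rate can move.

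**Classification of Stage 2 run-in exits**

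| Exit in the run-in | In the Aim 7a denominator? | In the Aim 7a numerator? |
|---|---|---|
| Subject actively withdraws | Yes | Yes |
| Recorded as lost to follow-up | Yes | Yes |
| Does not attend in-person baseline, withdrawn by staff | Yes | No |
| Withdraws or is lost, and also misses baseline | Yes | Not settled: no precedence rule |

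**Inputs.** The Stage 2 minimum of 20 is from the Summary and Section 2, and replacement is from Section 3.3.1. The documents give no loss rates, so these are assumptions: k no-shows (0, 1, 2 or 5), all coded as staff withdrawals; d = 2 later withdrawals or losses to follow-up; no deaths, transplants or other staff or investigator withdrawals. E is the number enrolled.

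**Formulas.** Aim 7a rate = d/E. Rate with no-shows counted = (d + k)/E. Retention over all enrolled = completers/E. Intervals are exact (Clopper-Pearson) 95%.

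**No replacement, E = 20, completers = 18 − k**

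| k | Aim 7a | No-shows counted | Retention over enrolled |
|---|---|---|---|
| 0 | 2/20 = 10% | 2/20 = 10% | 18/20 = 90% |
| 1 | 2/20 = 10% | 3/20 = 15% | 17/20 = 85% |
| 2 | 2/20 = 10% | 4/20 = 20% | 16/20 = 80% |
| 5 | 2/20 = 10% | 7/20 = 35% | 13/20 = 65% |

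The interval for 2/20 is 1.2% to 31.7%; for 7/20 it is 15.4% to 59.2%.

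**All losses replaced until 20 complete, E = 20 + 2 + k = 22 + k.** This takes the replacement rule to cover staff-withdrawn no-shows as well as later losses.

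| k | Aim 7a | No-shows counted | Retention over enrolled |
|---|---|---|---|
| 0 | 2/22 = 9.1% | 2/22 = 9.1% | 20/22 = 90.9% |
| 1 | 2/23 = 8.7% | 3/23 = 13.0% | 20/23 = 87.0% |
| 2 | 2/24 = 8.3% | 4/24 = 16.7% | 20/24 = 83.3% |
| 5 | 2/27 = 7.4% | 7/27 = 25.9% | 20/27 = 74.1% |

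At k = 5 the intervals are 0.9% to 24.3% for Aim 7a, 11.1% to 46.3% with no-shows counted, and 53.7% to 88.9% for retention. Run-in completion would be 22/27 = 81.5% (61.9% to 93.7%).

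**Coding alone.** Take the same 27 enrolled, with 5 run-in losses and 2 later ones, and let m of the 5 be coded as staff withdrawals. Aim 7a is then (7 − m)/27: 25.9% for m = 0, 5/27 = 18.5% for m = 2, and 7.4% for m = 5. The same events give different rates because precedence is not stated.

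**The case against.** **Some run-in loss does count.** A reader might infer that the drop-out rate cannot register run-in disengagement at all. The text does not support that. Subjects who say they are leaving, or who are recorded as lost to follow-up, are counted. It can also be argued that Aim 7a classifies by cause, and that the staff withdrawal is only the administrative act that follows. That reading is possible, but Section 4.3.1 makes withdrawal by staff the disposition, and Aim 7a excludes that category by name. A bare no-show, coded as directed, is not counted.

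**Primary retention captures the loss.** A reader might infer that the primary outcome is biased too. On the natural reading, with all enrolled subjects as denominator, it is not: someone who missed baseline has not completed all visits. The different starting points, baseline in Aim 1b and enrollment in Section 1.2, do not establish a bias either. Only if retention were computed among those reaching baseline would the no-shows disappear there (at k = 5 with replacement, 20/22 = 90.9% against 20/27 = 74.1%). The gap is an unwritten denominator.

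**The next trial would not necessarily be undersized.** A planner who used only Aim 7a in that scenario would consent 100/(25/27) = 108 people per 100 completers, against 100/(20/27) = 135 from retention. But no passage says Aim 7a will be used for sizing, and the primary outcome supplies the second figure.

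**The shortfall can be broken down.** Aim 7a cannot be computed unless exits are classified, so the part that is neither retained nor dropped out can be split by exit code. This stands: what is missing is a commitment to report the split.

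**In-person and remote baseline may be two modes.** The in-person rule can be read as the default and the phone order as the fallback when procedures go remote. That is reasonable, but Section 4.3.1 states the withdrawal rule without that condition, so the passages need reconciling before anyone can say who is a no-show.

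**Conclusion.** The point holds for one group: Stage 2 subjects who consent, do not attend the in-person baseline, and are coded as staff withdrawals. They sit in the Aim 7a denominator and outside its numerator, so the rate understates disengagement in the run-in whenever there is at least one of them. With none, there is no gap.

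The direction follows from the definitions. The size rests on assumed counts. With 20 enrolled and no replacement, Aim 7a stays at 10% while the rate with no-shows counted is 15%, 20% or 35% for 1, 2 or 5 no-shows. With all losses replaced and 5 no-shows, it is 7.4% against 25.9%. Intervals at this sample size are wide and overlap, but the discrepancy comes from the definition and is not sampling error.

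The effect is confined to a secondary feasibility outcome, provided retention is computed over all enrolled. It is worth fixing because the run-in exists to test interest and the correction is nearly free.

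**What to change.** - **Aim 7a:** count Stage 2 baseline no-shows as drop-outs, or report them as a separate run-in-loss category by recorded reason. Keep deaths and documented non-behavioural reasons, such as a hospitalization that prevented the visit (Section 4.5), apart from both. State which code takes precedence when a subject who withdraws or is lost also misses baseline.
- **Run-in completion:** report baseline completers over all enrolled, including those later replaced, with an exact 95% interval.
- **Aim 1b:** state that the denominator is all enrolled subjects, including those later replaced.
- **Section 4.3.1:** reconcile the in-person withdrawal rule with the phone baseline order, since together they decide who is a no-show.

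The cost is a few sentences of wording and a recorded reason for each missed baseline visit. Enrollment and withdrawal data are already needed for the existing aims. The reported drop-out rate may look less favourable.
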